9.8. Interim Analysis

There is no planned interim analysis for this study.

9.9. Other Topics

9.9.2. Pharmacokinetic Analysis

PK parameters including, but not limited to area under the concentration time curve (AUC), maximum plasma concentration of drug (C_{max}), time to maximum plasma concentration of drug (T_{max}) will be estimated for each subject. Descriptive statistics will be provided for all concentration data and PK parameters.

Full details will be included in the SAP.

9.9.3. Exploratory Analysis

Descriptive statistics will also be provided for exploratory parameters (eg, GDF11, SF3B1, C-reactive protein, SARS-CoV-2 antibody, and other molecular markers). Statistical tests will be applied for these parameters if applicable. Full details will be included in the SAP.

9.9.4. Subgroup Analysis

Appropriate subgroup analyses by baseline endogenous EPO level of < 500 U/L versus \geq 500 U/L and other baseline characteristics for clinical activity may be conducted as exploratory analyses. Full details will be included in the SAP.

10. ADVERSE EVENTS

10.1. Monitoring, Recording and Reporting of Adverse Events

An AE is any noxious, unintended, or untoward medical occurrence that may appear or worsen in a subject during the course of a study. It may be a new intercurrent illness, a worsening concomitant illness, an injury, or any concomitant impairment of the subject's health, including laboratory test values (as specified by the criteria in Section 10.3), regardless of etiology. Any worsening (ie, any clinically significant adverse change in the frequency or intensity of a pre-existing condition) should be considered an AE. A diagnosis or syndrome should be recorded on the AE page of the eCRF rather than the individual signs or symptoms of the diagnosis or syndrome.

Abuse, withdrawal, sensitivity or toxicity to an investigational product should be reported as an AE. Overdose, accidental or intentional, whether or not it is associated with an AE should be reported on the overdose eCRF (See Section 7.2.3 for the definition of overdose). Any sequela of an accidental or intentional overdose of an investigational product which meets the definition of an adverse event, should be reported as an AE on the eCRF. If the sequela of an overdose meets serious criteria, then it must be marked as serious on the eCRF. The overdose itself should not be reported as an AE.

In the event of overdose, the subject should be monitored as appropriate and should receive supportive measures as necessary. There is no known specific antidote for luspatercept overdose. Actual treatment should depend on the severity of the clinical situation and the judgment and experience of the treating physician. Phlebotomy may be performed if excessively high Hgb levels occur.

All subjects will be monitored for AEs during the study. Assessments may include monitoring of any or all of the following parameters: the subject's clinical symptoms, laboratory, pathological, radiological or surgical findings, physical examination findings, or findings from other tests and/or procedures.

All AEs will be recorded by the investigator from the time the subject signs informed consent until 42 days after the last dose of IP as well as those SAEs made known to the investigator at any time thereafter that are suspected of being related to IP. All adverse events (serious/non-serious) will be recorded on the eCRF and in the subject's source documents. Refer to Section 10.5 for instructions on how to report SAEs to Drug Safety.

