	Hematologic improvement in erythroid response (HI-E) per IWG (Cheson, 2006)	Proportion of subjects achieving HI-E over any consecutive 56-day period in the absence of RBC transfusions	W1D1 through Week 48
	Time to HI-E	Time from first dose to first onset of achieving ≥ 1.5 g/dL increase in hemoglobin over any consecutive 56-day period in the absence of RBC transfusions	W1D1 through Week 24; W1D1 through Week 48
	Time to mHI-E	Time from first dose to first onset of achieving ≥ 1.5 g/dL mean increase in Hgb compared to baseline over any consecutive 56-day period in the absence of RBC transfusions	W1D1 through Week 24; W1D1 through Week 48
	Duration of HI-E	Maximum duration of achieving ≥ 1.5 g/dL increase in hemoglobin for subjects who achieve Hgb increase ≥ 56 days in the absence of RBC transfusions	W1D1 through EOT
	Duration of mHI-E	Maximum duration of achieving ≥ 1.5 g/dL mean increase in Hgb compared to baseline for subjects who achieve mean Hgb increase ≥ 56 days in the absence of RBC transfusions	W1D1 through EOT
	RBC-TI	Proportion of subjects who maintain RBC-TI from W1D1 through Week 24, 48, and 72.	W1D1 through Week 24; W1D1 through Week 48; W1D1 through Week 72
	Safety	Type, frequency, severity of AEs and relationship of AEs to luspatercept	Screening through 42 days post last dose
	PK	C_{\max} , AUC, T_{\max}	W1D1 through 1-year post first dose

Table 2: Study Endpoints (Continued)

Endpoint	Name	Description	Timeframe
Secondary	Antidrug antibodies (ADA)	Frequency of antidrug antibodies and effects on efficacy, or safety, or PK	W1D1 through 1-year post first dose
	Progression to AML	Number and percentage of subjects progressing to AML; time to AML progression	W1D1 through 5 years from first dose or 3 years from last dose (whichever occurs later)
	Overall survival	Time from date of W1D1 to death due to any cause	W1D1 through 5 years from first dose or 3 years from last dose (whichever occurs later)
Exploratory	Molecular and cellular markers in the bone marrow and/or in peripheral blood	Evaluation of biomarkers that may potentially impact luspatercept efficacy, predict response or relapse, help to better understand MOA and/or provide further prognostic classification of MDS subtypes. Molecular markers (eg, SF3B1) include evaluation of MDS-associated gene mutations and their impact on drug efficacy, clinical response or relapse, disease progression, drug MOA and prognostication of MDS.	Baseline through End of Treatment

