Adverse events	6.1.19/10	Continuous, after signing informed consent until 42 days after last IP administration								—	—	—	

Table 3: Table of Events (Continued)

		Screening	Treatment Period							Post-treatment Follow-up		
								Efficacy Assessment Independent of any dose delays				
Section	Day -35 to -1	W1D1 Visit	W2D1 Visit	W3D1 Visit	3-wkly Visits W4D1 W7D1 W10D1 etc.	Other Visits	24-Wk MDS Assessment Visit D169	Every 24 wks D337 D505 etc.	EOT Visit ^a	42-Day Follow-up	Long Term Follow-up	End of Study
Section										6.2.2/11.1	6.3.1	6.3.2
Time window				±2 days	±2 days	±2 days	±2 days	±14days ^b	±14days ^b		+2 days	±7 days
SAFETY ASSESSMENTS (Continued)												
Prior and Concomitant medications/ procedures	6.1.18/8	Continuous, 8 weeks prior to W1D1 until 42 days after last IP administration or until the EOT Visit, whichever occurs later									—	—
Vital Signs (Height to be measured only at screening)	6.1.6	X	X	X	X	X	—	X	X	X	—	—
Serum Chemistry ^c	6.1.10	X	X	—	—	X	—	X	X	X	—	—

Table 3: Table of Events (Continued)

		Screening	Treatment Period								Post-treatment Follow-up		
									Efficacy Assessment Independent of any dose delays				
Section	Day - 35 to -1	W1D1 Visit	W2D1 Visit	W3D1 Visit	3-wkly Visits W4D1 W7D1 W10D1 etc.	Other Visits	24-Wk MDS Assessment Visit D169	Every 24 wks D337 D505 etc.	EOT Visit ^a	42-Day Follow-up	Long Term Follow-up	End of Study	
Section										6.2.2/11.1	6.3.1	6.3.2	11.2
Time window			±2 days	±2 days	±2 days	±2 days	±14days ^b	±14days ^b		+2 days	±7 days		
EFFICACY ASSESSMENTS													
Hematology ^c	6.1.9	X	X	X	X	X	X	–	X	X	X	–	–
Serum EPO	6.1.11	X	–	–	–	–	Every 6 weeks: ie, W7D1 W13D1 etc.	–	X	X	X	–	–
Serum Ferritin and other iron-related markers	6.1.12	X	X	–	–	X	–	X	X	X	–	–	–
Transfusion Data Collection and Assessment	6.4.1	Assess and record on ongoing basis (prior to each dose of IP) until 8 weeks after last dose of IP or the End of Treatment Visit, whichever occurs later. Clinical site staff must confirm (and document in the subject's source record) if any transfusions were received by the subject (including any at outside local institutions in between study visits) prior to each IP administration. In addition to local procedures in place at the site to capture this information, a patient transfusion diary will be provided to subjects and will be reviewed by the site when/if returned by the subject.										–	–

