6.3. Post-Treatment Follow-up Period

6.3.1. Safety Follow-up (42-Day Follow-up)

All subjects will be followed for 42 days after the last dose of IP for AE reporting, as well as SAEs made known to the investigator at any time thereafter that are suspected of being related to IP, as described in Section [10.1](#).

Refer to [Table 3](#) for additional assessments to be performed at the 42-Day Follow-up.

Females of childbearing potential must avoid becoming pregnant for 12 weeks after the last dose of IP and male subjects must avoid fathering a child for 12 weeks after the last dose of IP. Refer to Section [10.4](#) for additional details.

In the case of dose delays that exceed 6 weeks (+2 days) and end in treatment discontinuation, the 42-Day Follow-up Visit will be omitted and replaced by the EOT Visit.

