AE = adverse event; Hgb = hemoglobin; IP = investigational product; IWG = International Working Group; MDS = myelodysplastic syndromes; RBC = red blood cell.

^a Possibly, probably or definitely related to IP.

^b Includes systolic blood pressure ≥ 160 mmHg and diastolic blood pressure ≥ 100 mmHg.

^c If dose delay is > 12 consecutive weeks (> 15 weeks from last dose administered), treatment should be discontinued.

^d Predose Hgb value not being influenced by RBC transfusion (ie, Hgb result > 14 days after last RBC transfusion or within 3 days from next RBC transfusion); Hgb should be rechecked weekly during dose delay.

^e Upper limit of normal $> 10,000$ total WBC/ μ L or as defined by institutional standards.

^f Peripheral blood smear should be prepared for central pathology lab assessment.

^g At the investigator's discretion, bone marrow samples may also be collected and analyzed centrally to assess MDS disease status (eg, cytromorphology) prior to making decision regarding treatment discontinuation. The central laboratory must also confirm $< 5\%$ bone marrow blasts prior to resumption of treatment.

^h The investigator may contact the Medical Monitor prior to making decision regarding treatment discontinuation.

ⁱ Every attempt should be taken to assess the blasts count in peripheral blood prior to dosing, however, in circumstances where results are not readily available at the time of planned dosing, the investigator may proceed with dosing provided there are no signs of clinical progression. In this case, results must be evaluated as soon as they become available (but no later than 3 days post dosing). If presence of $\geq 1\%$ blasts in peripheral blood is observed, actions described in table above must be followed immediately.

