8. CONCOMITANT MEDICATIONS AND PROCEDURES

Over the course of this study, additional medications may be required to manage aspects of the disease state of the subjects, including side effects from trial treatments or disease progression. Supportive care may be administered at the discretion of the investigator.

All prior/ concomitant medications, used 8 weeks prior to W1D1 until 42 days after the last dose of IP (or until the EOT Visit, whichever occurs later), must be reported on the eCRF. All prior procedures within the 8 weeks prior to W1D1 as well as concomitant procedures (including transfusions) will be recorded on the appropriate eCRF(s).

Prior anticancer treatments should be recorded on the appropriate eCRF(s) regardless of treatment discontinuation/procedure date.

Prior ESAs and G-CSF/GM-CSF should be recorded on the appropriate eCRF(s) regardless of treatment discontinuation date.

If a subject requires treatment with any new medications that are specifically excluded in Section 8.2, the subject will be discontinued from treatment and should complete the EOT visit and enter the Post-Treatment Follow-up Period of the study. The investigator should consult the medical monitor regarding any questions about whether a new medication or dosage of existing medication would require the subject to discontinue from the study.

For information regarding other drugs that may interact with IP and affect its metabolism, pharmacokinetics, or excretion, please see the IB and/or package insert.

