10.6. Reporting of Serious Adverse Events

Any AE that meets any serious criterion requires reporting as an SAE within 24 hours of the investigator's knowledge of the event. This instruction pertains to initial SAE reports as well as any follow-up reports.

This requirement applies to all SAEs (regardless of relationship to IP) that occur during the study (from the time the subject signs informed consent until 42 days after the last dose of IP) or any SAEs made known to the investigator at any time thereafter that are suspected of being related to IP. Serious adverse events occurring prior to treatment (after signing the ICF) are to be recorded within the eCRF, but do not require reporting to Celgene Drug Safety.

Where required by local legislation, the investigator is responsible for informing the Institutional Review Board/Ethics Committee (IRB/EC) of the SAE and providing them with all relevant initial and follow-up information about the event. The investigator must keep copies of all SAE information on file including correspondence with Celgene and the IRB/EC.

The SAE is recorded within the eCRF, and the data are transmitted electronically to Celgene Drug Safety. In the event electronic transmission is not available, a paper SAE Report Form will be completed and sent directly to Celgene Drug Safety, ensuring the event is recorded on the eCRF as well.

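### When a dose hold ends in discontinuation more than 42 days after the last dose, the AE window does not require non-serious AEs, or most SAEs not suspected as related, to be recorded up to the EOT Visit

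*Combined protocol and SAP*

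**What the plan says.** All statements of the general AE window end at the same point.

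- Section 10.1: AEs are recorded "until 42 days after the last dose of IP as well as those SAEs made known to the investigator at any time thereafter", the later SAEs being limited to those "that are suspected of being related to IP".
- Section 10.6 (SAEs regardless of relationship): "from the time the subject signs informed consent until 42 days after the last dose of IP".
- Table 2, Safety timeframe: "Screening through 42 days post last dose".
- Table 3, AE row: "Continuous, after signing informed consent until 42 days after last IP administration".
- Section 6.3.1 gives the same 42 days.

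Holds can last longer than that. Table 5 footnote c reads: "If dose delay is > 12 consecutive weeks (> 15 weeks from last dose administered), treatment should be discontinued". Section 6.3.1 provides for the case: "In the case of dose delays that exceed 6 weeks (+2 days) and end in treatment discontinuation, the 42-Day Follow-up Visit will be omitted" and is replaced by the EOT Visit. It does not extend AE recording to that visit.

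Other data are extended. Section 8 collects medications "used 8 weeks prior to W1D1 until 42 days after the last dose of IP (or until the EOT Visit, whichever occurs later"). Section 6.4.1 collects transfusions to the later of 8 weeks after the last dose and the EOT Visit.

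**The concern.** A subject on hold has not yet been discontinued and is still under study care, but a window counted only from the last dose can close before the EOT Visit. The last dose is known to be the last only in retrospect, so whether an event belongs in the data depends on whether the subject is later re-dosed.

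Three other parts of the protocol assume the opposite:

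- The Protocol Summary (Post-Treatment Follow-up Period) lists AE collection among the EOT and 42-Day evaluations.
- Table 3 schedules a physical examination at EOT, and Section 6.1.5 requires significant findings to be reported as AEs.
- Section 9.7 plans a summary of treatment-emergent AEs leading to discontinuation. A non-serious AE late in a hold that itself causes discontinuation would fall outside the window that feeds this summary.

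The database could also hold a medication started late in a hold without the AE that prompted it. The subjects concerned are those who never resume, including some held for related Grade 3 or higher toxicity.

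**Working it through.** **Inputs**

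- End of general AE window: Day 42 after the last dose (10.1, 10.6, 6.3.1, Tables 2 and 3).
- Longest delay under footnote c: 12 consecutive weeks, stated as 15 weeks from the last dose (Table 5).
- Dosing interval: 21 days (7.2.1).
- Planned enrollment: approximately 20 (4.1).

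**1. Reproduce the plan's figure.** 12 x 7 + 21 = 84 + 21 = 105 days, and 105 / 7 = 15 weeks. Footnote c agrees with itself and counts the delay from the missed due date.

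**2. Size of the gap.** If the EOT Visit falls on day D after the last dose, the uncovered time is D - 42:

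- D = 56 (week 8): 14 days
- D = 84 (week 12): 42 days
- D = 105 (week 15): 63 days, or 63 / 105 = 60% of the time since the last dose

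With an end point at the later of Day 42 and EOT, the gap up to EOT is 0 for every D.

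**3. Where the limit applies.** Footnote c is attached only to the row for related AEs of Grade 3 or higher. The row for predose hemoglobin of 12.0 g/dL or more states no maximum, so 63 days is not a ceiling there.

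**4. The threshold in 6.3.1.** Six weeks plus 2 days is 6 x 7 + 2 = Day 44 if counted from the last dose, or 21 + 44 = Day 65 if counted from the missed dose. The section does not say which. On either reading AE recording is not extended.

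**5. Dependence on the future.** Take a non-serious AE on Day 60 of a hold. If the subject is re-dosed on Day 70, the window runs to at least Day 70 + 42 = Day 112 and the event is inside it. If the subject is instead discontinued on Day 70, the window closed on Day 42 and the event is 60 - 42 = 18 days outside it.

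**6. What is still collected after Day 42**

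- SAEs suspected as related, without time limit (6.3.1, 10.1, 10.6).
- New malignancy, pre-malignancy and AML progression regardless of causality, through long-term follow-up (6.1.20, 10.5).
- Date and cause of death (6.3.2).
- Pregnancies to 12 weeks after the last dose (10.4.1).

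This leaves uncovered non-serious AEs of any causality, and SAEs not suspected as related other than those listed.

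**7. Scale.** One subject-level event among 20 is 1 / 20 = 5 percentage points of incidence, and only if that subject had no earlier event of the same type. This shows the scale of one event; it does not estimate the loss.

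**The case against.** The strongest reply is that little is lost in practice. Nobody knows that a dose is the last while a hold is open. Section 6.2 has AEs assessed on an ongoing basis, the note to Table 3 enters monitoring during delays as unscheduled visits, and Section 10.1 has all subjects monitored for AEs during the study. Nothing tells sites to stop recording or to delete entries. The toxicity that triggers a hold will usually be found by the next dosing visit, around Day 21, inside the window. Section 6.2.2 places EOT as soon as possible after the decision to discontinue, so a decision made by Day 42 leaves little or no gap. A fixed window from the last dose also gives every subject the same off-drug observation time, which is a defensible choice.

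Much of this stands. It makes 63 days a limit derived from the text, not an expected loss. It does not remove the mismatch: the text does not require late events to be kept once a hold ends in discontinuation, and the EOT provisions in the Protocol Summary and Section 6.1.5 conflict with the window without amending it.

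A reader might infer that AE and SAE recording stops altogether at Day 42. The exceptions in step 6 contradict that. A reader might also infer that the safety endpoint is biased downward in the subjects who tolerated treatment worst. The documents do not show this: the triggering event is usually captured, and Section 9.7 leaves full details to an SAP whose definition of treatment-emergent is not in the supplied text.

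**Conclusion.** The gap is real but narrow. For holds that end in discontinuation after Day 42, the stated window does not require non-serious AEs, or SAEs not suspected as related (apart from the exceptions in step 6), between Day 43 and the EOT Visit. The gap is up to 63 days for the Table 5 row that carries footnote c, taking EOT at Day 105; any lag from decision to visit would add to it. For the hemoglobin hold no upper bound can be derived.

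The conclusion rests on reading the windows literally. The number of subjects affected and the effect on the treatment-emergent tables cannot be determined from the documents, and no direction of bias is established. The change is still worth making, because it resolves a conflict between sections and makes inclusion of an event independent of later re-dosing.

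**What to change.** In Sections 10.1, 10.6 and 6.3.1, the Safety row of Table 2 and the AE row of Table 3, end AE collection at the later of 42 days after the last dose and the EOT Visit. This is the rule that Section 8 and Table 3 already apply to concomitant medications. Keep the provision for suspected-related SAEs at any later time. Define the treatment-emergent window for Section 9.7 to match. Section 10.8 ends COVID-19 reporting at the same 42 days and should be checked for consistency.

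Off-drug observation would then differ between subjects (up to 105 days at the footnote c limit against 42 days), so also present AE incidences restricted to 42 days after the last dose.

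The cost is the text edits and eCRF guidance, a few more AE records, unequal off-drug observation time in the main tables, and one extra table. No visit is added, because the EOT Visit already takes place, and no dosing or hold rule changes.

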10.2. Evaluation of Adverse Events

A qualified investigator will evaluate all adverse events as to:

10.2.1. Seriousness

An SAE is any AE occurring at any dose that:

- Results in death;
- Is life-threatening (ie, in the opinion of the investigator, the subject is at immediate risk of death from the AE);

- Requires inpatient hospitalization or prolongation of existing hospitalization (hospitalization is defined as an inpatient admission, regardless of length of stay);
- Results in persistent or significant disability/incapacity (a substantial disruption of the subject's ability to conduct normal life functions);
- Is a congenital anomaly/birth defect;
- Constitutes an important medical event.

Important medical events are defined as those occurrences that may not be immediately life-threatening or result in death, hospitalization, or disability, but may jeopardize the subject or require medical or surgical intervention to prevent one of the other outcomes listed above.

Medical and scientific judgment should be exercised in deciding whether such an AE should be considered serious.

Events **not considered** to be SAEs are hospitalizations for:

- a standard procedure for protocol therapy administration. However, hospitalization or prolonged hospitalization for a complication of therapy administration will be reported as an SAE.
- routine treatment or monitoring of the studied indication not associated with any deterioration in condition.
- the administration of blood or platelet transfusion as routine treatment of studied indication. However, hospitalization or prolonged hospitalization for a complication of such transfusion remains a reportable SAE.
- a procedure for protocol/disease-related investigations (eg, surgery, scans, endoscopy, sampling for laboratory tests, bone marrow sampling). However, hospitalization or prolonged hospitalization for a complication of such procedures remains a reportable SAE.
- hospitalization or prolongation of hospitalization for technical, practical, or social reasons, in absence of an AE.
- a procedure that is planned (ie, planned prior to start of treatment on study); must be documented in the source document and the eCRF. Hospitalization or prolonged hospitalization for a complication remains a reportable SAE.
- an elective treatment of or an elective procedure for a pre-existing condition, unrelated to the studied indication, that has not worsened from baseline.
- emergency outpatient treatment or observation that does not result in admission, unless fulfilling other seriousness criteria above.

For each AE, the investigator will provide information on severity, start and stop dates, relationship to the IP, action taken regarding the IP, and outcome.

